6.2. Efficacy Endpoints

Unless otherwise specified, the efficacy evaluation period will be the observation period in Section 2.2. The number of days from the start date of treatment to the onset date of event will be calculated as [event onset date – start date of treatment with this drug + 1]. In the analyses related to the end date of the observation period, the primary definition of the end date will be up to Day 28 after the end of treatment, and the secondary definition will also be defined for evaluation (Section 10.2 Table 2).

The following efficacy endpoints are defined for Efficacy Analysis Sets 1, 2, and 3.

• Worsening of severity of infection caused by SARS-CoV-2: Whether the severity of infection caused by SARS-CoV-2 has worsened will be evaluated. However, when the severity is severe at the start of this drug and does not worsen during the observation period, it will be considered as "severe at the start of treatment." Otherwise, if the date of the highest severity is the day after the end of the evaluation period or later, it will be handled as "unknown (highest severity recorded after the end of evaluation period)." Therefore, the categories will be as follows. "Worsened" will be considered as an

event. The expected entries in the CRF and their handling, and assessment of endpoints are shown in Section 10.3 Table 3.

- Not worsened, worsened, severe at the start of treatment, unknown (highest severity recorded after the end of the evaluation period, worsening unknown, no record of worsening)
- Highest severity: The highest severity will be evaluated for patients with the above worsening of severity of infection caused by SARS-CoV-2. If the highest severity is unknown but the severity is considered to have worsened, the highest severity will be "moderate II or severe (indistinguishable)" for patients with the initial severity of moderate I and as "severe" for patients with the initial severity of moderate II. It consists of the following categories. The expected entries in the CRF and their handling, and assessment of endpoints are shown in Section 10.3 Table 3.
 - Mild, moderate I, moderate II, severe, moderate II or severe (indistinguishable), unknown (severity unknown, severity not recorded)

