10.2. Appendix 2: Data Extraction Details

 Table 2.
 Definitions of Acceptable Windows for Timing

Timing	Endpoint	Definition [acceptable window]
At the start of treatment	Efficacy endpoints, viral load, body temperature, percutaneous arterial oxygen saturation	From 30 days prior to the date of first dose in this study (start date of treatment) to the start date of treatment
During the observation period	Safety endpoints, efficacy endpoints, viral load, body temperature, percutaneous arterial oxygen saturation, concomitant drug therapy, and non-drug therapy	Start date of treatment to Day 28 after the end of treatment
End date of the observation	Efficacy endpoints	Primary definition: Up to Day 28 after the end of treatment
period		Secondary definition 1: Up to 42 days after the end of treatment
		Secondary definition 2: Entire period

10.3. Appendix 3: Data Entries Related to Efficacy Endpoints and Their Handling, and Assessment of Endpoints

Table 3. Worsening of Severity and Highest Severity of Infection Caused by SARS-CoV-2

Symptoms	Severity at			Worsening of	of severity: H	ighest sev	erity			
at the start of	the start of treatment	Worsening	Vorsening of severity during the observation period							
treatment	with this	Absent		Present						
with this	drug	Highest seve	erity	ity						
drug		NA	Mild	Moderate I	Moderate II	Severe	Unknown	NA		
Absent	NA	Absent: NA	Present: Mild	Present: Moderate I	Present: Moderate II	Present: Severe	Present: Unknown	Unknown: NA		
Present	Mild		Case 1				Case 2			
	Moderate I									
	Moderate II									
	Severe	Severe at the start: NA	Case 3							
	Unknown	Absent: NA	Case 4							
Unknown	NA	Case 5								

NA: not applicable

Discrepancies between evaluations at the start of treatment with this drug and during the observation period are subject to re-investigation, but the reasons for being subject to re-investigation and handling of cases where there is no change as a result of re-investigation are shown below.

- Case 1: Assessed as "Unknown: NA" because the highest severity is lower than the severity at the start of treatment with this drug.

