- Case 2: Assessed as "Unknown: NA" because the severity during the observation period is unknown. However, if the severity is considered to have worsened during the observation period, it will be handled as "Present: Unknown" for analysis. In addition, when the severity at the start is moderate I, the highest severity will be considered as "moderate II or severe (indistinguishable)" for analysis, and when the severity at the start is moderate II, the highest severity will be considered as "Present: Severe" for analysis.
- Case 3: Assessed as "Unknown: NA" because the severity is severe at the start but worsened during the observation period. However, if the severity is assessed as severe at the start, worsening of severity will be handled as "sever at the start" and the highest severity will be handled as NA.
- Case 4: Assessed as "Unknown: NA" because the severity at the start is unknown. However, if the severity is judged to have worsened during the observation period, worsening of severity will be handled as "present" and the highest severity entered will be the highest severity for analysis.
- Case 5: Assessed as "Unknown: NA" because the symptoms at the start are unknown.

Table 4. Resolution of symptoms from the start of treatment with this drug as of the end date of the observation period

Symptoms at the	Resolu	ition of symp	toms						
start of treatment	Symptoms at the end of the								
with this drug	observation period								
	Absent	Absent Present Unknown							
Absent	No								
	symptoms at								
	the start of								
	treatment	t Absent Unknown							
	with this								
	drug								
Present	Present								
Unknown	Unknown								

Table 5. Improvement in severity from the start of treatment with this drug as of the end date of the observation period

Symptoms	Severity at	Improvement in severity								
at the start	the start of	Symptoms a	Symptoms at the end date of the observation period							
of	treatment	Absent	Absent Present							
treatment	with this	Severity at t	the end da	te of the ob	servation p	eriod				
with this	drug	NA	Mild	Moderate	Moderate	Severe	Unknown	NA		
drug				I	II					
Absent	NA	No symptom	ns at the sta	art of treatme	ent with this	drug				
Present	Mild	Present	Absent							
	Moderate I									
	Moderate									
	П									
	Severe									
	Unknown									
Unknown	NA	Unknown	•				•

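### SAP Table 3 discards a recorded worsening when baseline symptoms are unknown (Case 5) but keeps it when only the baseline grade is unknown (Case 4), without giving a reason

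*SAP*

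**What the plan says.** Worsening is a direct CRF entry. Under Protocol Section 8.3.9 the investigator records whether the disease worsened after administration, the date of the peak and the highest severity.

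SAP Section 6.2 sorts this entry into four categories: not worsened, worsened, severe at the start of treatment, and unknown. Three grounds stand in brackets after 'unknown': "highest severity recorded after the end of the evaluation period, worsening unknown, no record of worsening". The same paragraph says that the expected CRF entries, their handling "and assessment of endpoints are shown in Section 10.3 Table 3".

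The notes to Table 3 in SAP Section 10.3 cover discrepant entries that have already been queried. They set out the "handling of cases where there is no change as a result of re-investigation are shown below". Two notes matter here:

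- **Case 4** (symptoms present, baseline grade unknown): the default is unknown, but a worsening that the physician recorded is then scored as present. On the grade, the note says that "the highest severity entered will be the highest severity for analysis".
- **Case 5** (baseline symptoms unknown): unknown "because the symptoms at the start are unknown". The note ends there.

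Both highest-severity endpoints in Section 6.2 are evaluated only in patients classed as worsened. For worsening, Section 8.2.4.1 takes the frequency and proportion of every category. For highest severity it divides by the number of patients with worsening.

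**The concern.** Two patients can have the same CRF entry after treatment, namely worsening present with a severe peak inside the window. One counts as an event and the other does not, depending on which baseline item is missing. The entry that is overridden is an adverse outcome that the physician observed and recorded, so overriding it can only make the drug look better on 'worsened'.

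These patients are foreseeable. SAP Section 8.2.2.1 plans an unknown level for baseline symptoms, and Protocol Section 8.9 names missing chart data as a limitation. The planned sensitivity analyses change the end-date window (SAP Section 8.2.4) and the definition of hospitalization (Section 8.2.4.6). Neither would show the effect of Case 5.

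**Working it through.** **1. One entry, every baseline state.** Take the entry 'worsening present, highest severity moderate II or severe', dated inside the window, and apply Table 3 with its notes.

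| Baseline symptoms | Baseline grade | Worsening status |
|---|---|---|
| Absent | not applicable | Present, event |
| Present | mild, moderate I or moderate II | Present, event (subject to Case 1 if the recorded peak is below baseline) |
| Present | severe | Severe at the start (Case 3) |
| Present | unknown | Present, event (Case 4) |
| Unknown | not applicable | Unknown (Case 5) |

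A patient with unknown baseline symptoms either had none or had symptoms of a grade not known. Table 3 returns an event for the first state and, under Case 4, for the second. Not knowing which of the two applies returns no event. Case 2, where the highest severity is unknown, also keeps a recorded worsening. Case 5 is the only missing-information case that does not. Its cell appears to span the whole row, so a recorded absence of worsening becomes unknown too.

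**2. Effect on the proportion 'worsened'.** The plan gives no worsening rate and no count of Case 5 patients, so there is no figure of its own to reproduce. Assumptions: N = 3000 (the target for the safety analysis set, used here for Efficacy Analysis Set 1), true worsening 2%, Case 5 share u, equal risk, and unknown patients kept in the denominator.

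Events = 3000 × 0.02 = 60. Lost = 60 × u. Reported proportion = (60 − lost) / 3000.

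| u | Lost | Reported |
|---|---|---|
| 1% | 0.6 | 1.98% |
| 2% | 1.2 | 1.96% |
| 5% | 3.0 | 1.90% |
| 10% | 6.0 | 1.80% |

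For scale, the standard error in events is √(3000 × 0.02 × 0.98) = 7.7. The exact 95% interval is 1.53% to 2.57% for 60/3000 and 1.36% to 2.34% for 54/3000.

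Other assumed rates, over the same range of u: at 1% worsening, 0.3 to 3 of 30 events are lost; at 5%, 1.5 to 15 of 150.

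Unequal risk: if Case 5 patients have three times the risk and u = 5%, the risk in the others is 0.02 / (0.95 + 0.05 × 3) = 1.82%. The loss is 150 × 3 × 0.0182 = 8.2 events, and the reported proportion is 51.8 / 3000 = 1.73%.

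**3. Effect on highest severity.** Let W patients have worsened, M of them to moderate II or severe, and let Case 5 remove w and m of these. The proportion moves from M/W to (M − m)/(W − w). It falls if m/w exceeds M/W, rises if m/w is smaller, and otherwise stays the same. With W = 60 (2%), M = 30 (1%) and w = 3, the proportion of 50% becomes 27/57 = 47.4% if all three were moderate II or severe, and 30/57 = 52.6% if none was. The count M cannot rise. The direction of the proportion is open.

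**4. Effect on the subgroup.** SAP Section 5.4 has one level for unknown symptoms or unknown severity at baseline. It pools Case 4 patients, who can have events, with Case 5 patients, who cannot. If a fraction c of the level is Case 5 and risks are equal, the observed risk, and hence the risk ratio for worsening in Section 8.2.4.7, is multiplied by (1 − c).

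**The case against.** **Section 6.2 defers to Table 3.** A reader might infer that the appendix flatly contradicts the definition. The documents do not support that. Section 6.2 refers to Table 3 for handling, and its bracketed grounds are not said to be exhaustive. Case 1 also sends a recorded worsening to unknown. This stands: the fault is an unexplained difference between a definition and its appendix.

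**Case 5 lacks more information than Case 4, and declining to assign an event is cautious.** The first half is true. But the reason for caution, that the patient may already have been severe or above the recorded peak at baseline, applies equally in Case 4, where the entry is accepted. Dropping recorded worsening favours the drug, so the choice is not conservative.

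**Tables 4 and 5 also set unknown baseline symptoms to unknown.** Resolution and improvement from the start of treatment are defined by comparison with baseline and cannot be scored without it. Worsening is recorded directly, so those tables are no precedent.

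**The moderate II or severe rate.** A reader might infer that this proportion is biased down as well, or that three lost outcomes of this kind are to be expected at a 2% Case 5 share. Neither follows. Its stated denominator is patients with worsening. With 60 Case 5 patients at a 1% rate the expected loss is 60 × 0.01 = 0.6; losing three needs a risk of 3/60 = 5% in those patients, or a 10% share (300 × 0.01 = 3). No passage supports either.

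**Mitigation.** The rule applies only after re-investigation brings no change, the unknown category is displayed, and a listing of efficacy evaluation is planned (SAP Section 9). No endpoint is named primary and testing is exploratory. Death and hospitalization-or-death are unaffected. All of this stands and limits the size of the problem.

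**Conclusion.** The concern holds in limited form. Case 5 overrides a recorded, in-window worsening that Case 4 would accept, and the SAP gives no reason.

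- **'Worsened':** biased downward, on the reading that unknown patients stay in the denominator because 'unknown' is a tabulated category.
- **Highest severity:** recorded moderate II or severe outcomes are lost from the counts; the direction of bias in the proportion is not established.
- **Subgroup level for unknown symptoms or severity:** its risk ratio for worsening is diluted.

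The effect is probably small. At N = 3000, 2% worsening and equal risk, a Case 5 share of 1% to 10% costs 0.6 to 6 of 60 events, less than one standard error of the count. It would be larger only with a higher share or a higher risk in these patients, and the documents give counts for neither. The case for change is that the loss runs in one direction, falls on adverse outcomes and is cheap to prevent.

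**What to change.** Rewrite the Case 5 note so that it follows Case 4:

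- worsening recorded as present: handle as present, with the entered highest severity;
- worsening recorded as absent: handle as 'Absent: NA';
- 'Unknown: NA' only if the worsening item itself is unknown or blank, or the peak falls outside the evaluation window.

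Flag these patients in the separate list of data handling mentioned in SAP Section 7, so that the number with unverified baseline status is visible.

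If the sponsor prefers to keep Case 5, Section 6.2 should name unknown baseline symptoms as a ground for 'unknown' and say why. A sensitivity analysis should then count recorded worsening in these patients.

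The cost is one note and the matching derivation. The stated worsening rate may be slightly higher, and a few patients will count as worsened although their baseline state cannot be verified, as Case 4 already allows.
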